## Missing data

The number/frequency of missing values for the primary outcomes in each group at each time point will be provided. In the primary analysis, missing data are handled implicitly by maximum likelihood estimation in the linear mixed model and missing data will be assumed to be missing at random. This is equivalent to making multiple imputations for each treatment group separately and estimating the treatment effect that would have been found had all subject completed their assigned treatment (efficacy estimate) under the missing at random assumption.

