10.4 Continuous Glucose Monitoring

The iPro®2 CGM system will be used. The CGM will be inserted under the skin on the lower part of the abdomen (under the umbilicus) by the investigator or study personnel at V1 and V5 for use in a period of six days. Participants will receive a glucometer together with oral and written instructions about how to measure glucose levels four times a day while wearing the CGM. Measurements are to be taken before breakfast, before lunch, before main evening meal and before bedtime. Participants are asked to hand in the CGM together with the urine collection or at V2 after baseline measurements and by mail or in person after six days of use after V5.

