### Timing of outcome assessments

HbA1c was measured at the screening visit (V0), at the baseline visit (V1), after 12 weeks of intervention, after 24 weeks (V2) of intervention, and after six months follow-up (V3). MAGE was measured after the baseline visit (V1), and after 24 weeks of intervention (after V2).

See section 6: Analyses for timing of secondary/descriptive/explorative outcome assessments.

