### Completers and protocol deviations

**Completers:** Participants who participated in an assessment of at least one of the primary outcomes at V2 and/or V3.

**Lost to follow-up:** Participants who did not participate in assessment of primary outcomes at V2.

**Excluded for statistical data analyses:** Participants in the three study groups dropping out or lost to follow-up before baseline measurements have been collected.

**Protocol deviators:** None of the participants in the two study groups are considered protocol deviators.

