#### **Secondary/descriptive/exploratory outcomes**

The treatment effect will be given as the baseline corrected difference between the groups at V2 and V3. No minimal clinically relevant differences were defined for these outcomes.

- HbA1c, mmol/mol (only for V3)
- Blinded CGM data (not measured at V3)
  - Mean amplitude of glycaemic excursions (MAGE), mmol/l
  - Mean plasma glucose, mmol/l
  - Time in range (TIR): % of readings and time 3.9-10.0 mmol/l
  - Time above range (TAR): % of readings and time 10.1-13.9 mmol/l (level 1 – high)
  - Time above range (TAR): % of reading and time >13.9 mmol/l (level 2 – very high)
  - Time above range: % of readings and time >13.9 mmol/l
  - Time below range (TBR): % readings and time 3.0-3.8 mmol/l (level 1 – low)
  - Time below range (TBR): % readings and time <3.0 mmol/l (level 2 – very low)
  - Glycaemic variability, coefficient of variation (CV), %
- BMI (kg/m^2)
- Body weight (kg)
- Waist/Hip ratio, unitless
- Blood pressure
  - Systolic blood pressure (mmHg)
  - Diastolic blood pressure (mmHg)
- LDL cholesterol (mmol/l)
- Median carbohydrate estimation errors, g
- Median carbohydrate estimation errors, %
- Self-reported diabetes diet-related quality of life (DDRQOL), total score within each subscale
  - General perception of diet

- Satisfaction with diet
- Restriction of social functions
- Burden of dietary therapy
- Perceived benefits of dietary therapy
- Mental health
- Vitality
- Self-reported Perceived Health Competence in Diabetes Scale (PCDS), total score
- Self-reported Healthcare Climate Questionnaire (HCCQ) (not measured at V3), total score

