## Analysis methods

Analyses of the primary outcomes will be performed based on efficacy estimates.

Before further analysis and before unblinding, all variables will be inspected to detect outliers to uncover potential errors, such as registration errors.

All continuous outcomes covered by this SAP will as a rule be modelled using baseline corrected repeated measures regression (22) with the following fixed effects and interactions between fixed effects: Visit, Visit (factorial)\*Treatment. Data from V1, V2, and V3 will be included in the analysis. The models will be specified with a restricted maximum likelihood estimation method and a repeat on participant level (unstructured covariance structure). Model fit will be evaluated using graphical methods before estimating the treatment effects and if necessary, outcomes will be log-transformed. Estimated mean differences (CI95%) between groups (CI95%), conditional means (CI95%), and within group changes (CI95%) will be extracted from the model. For log-transformed outcomes the results will be back-transformed and be presented as the ratio between estimated mean differences (CI95%), estimated conditional geometric means (CI95%) and relative changes within groups (CI95%), respectively. If log-transformation cannot meet distribution assumptions, a generalized mixed linear model with an appropriate distribution will be applied instead of the repeated measures regression model. In case the distribution does not comply with the distributions available in the generalized mixed linear model a non-parametric test will be used to compare the change scores for the given outcome.

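### A participant with missing week-24 MAGE adds nothing to the planned MAGE group contrast, and the HbA1c that could help explain the gap is not used

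*SAP*

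**What the plan says.** SAP V2 is the week-24 visit (protocol V5), and SAP V3 is the week-48 visit (protocol V6).

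- **When MAGE is measured.** SAP, Timing of outcome assessments: "MAGE was measured after the baseline visit (V1), and after 24 weeks of intervention (after V2"). The list of secondary outcomes confirms that there is no later value: "Blinded CGM data (not measured at V3").
- **When HbA1c is measured.** Same SAP section: "HbA1c was measured at the screening visit (V0), at the baseline visit (V1), after 12 weeks of intervention, after 24 weeks (V2) of intervention", and again at V3.
- **The model.** SAP, Analysis methods, specifies a baseline-corrected repeated-measures regression for each continuous outcome "with the following fixed effects and interactions between fixed effects: Visit, Visit" by treatment, fitted by REML with an unstructured covariance. "Data from V1, V2, and V3 will be included in the analysis"; week 12 is not listed. HbA1c is not a covariate, co-outcome or auxiliary variable in the MAGE model.
- **Missing values.** SAP, Missing data: "missing data are handled implicitly by maximum likelihood estimation in the linear mixed model", assuming missing at random. The section likens this to imputing separately within each treatment group. The Additional analyses section plans nothing, so there is no missing-data sensitivity analysis.
- **Who counts as a completer.** SAP Section 4: "Participants who participated in an assessment of at least one of the primary outcomes at V2 and/or V3". HbA1c without MAGE is therefore an allowed pattern.
- **What each measurement demands.** Under Protocol 10.4, MAGE needs six days of sensor wear with four glucose measurements a day, and the week-24 device comes back "by mail or in person after six days of use after V5". HbA1c at that visit is part of the blood draw (Protocol 10.2 and 11.7).

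**The concern.** A likelihood-based mixed model helps with missing data when a participant who lacks the value of interest has other informative post-baseline values in the same model. For MAGE there are none. The likelihood, or the within-arm imputation that the SAP calls equivalent, can draw only on V1 MAGE.

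MAGE is also the more burdensome measurement, and the trial is open-label. Willingness to wear and return the sensor at week 24 could be related to how control has gone, and differently so by arm. HbA1c is the obvious marker of that. If so, the MAGE contrast is biased although the data that would largely correct it have been collected.

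The stakes come from the decision rule. SAP Section 2 allows a superiority claim on HbA1c or MAGE, and requires the estimate itself to reach 0.35 mmol/l for MAGE. A shift in the estimate acts directly on that threshold.

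**Working it through.** **1. The plan's own figure.** Protocol 13.3 uses a MAGE difference of 0.35 and SD 0.7 (standardised effect 0.5), two-sided 5%, 80% power. Normal approximation: n = 2 × (1.96 + 0.84)² × (0.7/0.35)² ≈ 62.8, so 63 per arm. The t-test version gives 63.8, so 64 per arm and 3 × 64 = 192, as in Table 5. With 64 per arm the SE is 0.7 × √(2/64) = 0.124, and the 95% interval excludes zero from about 1.96 × 0.124 = 0.24. The 0.35 requirement is therefore the binding condition.

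**2. What the MAGE model can use.** Write the joint density as f(V1) × f(V2 | V1), with a common V1 mean μ1 and E[V2 | V1, arm g] = μ2g + β(V1 − μ1) = αg + β·V1. The contrast μ2g − μ2c equals αg − αc, which appears only in the second factor. A participant with V1 MAGE only enters only the first factor and adds nothing to the contrast.

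Numerical check: one simulated three-arm data set, 77 per arm, SD 1.2, V1–V2 correlation 0.6, model fitted by REML.

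| Data | First contrast (SE) | Second contrast (SE) |
|---|---|---|
| 20% of V2 missing, all participants | −0.30693 (0.15556) | −0.14813 (0.15263) |
| Same, V1–V2 pairs only | −0.30693 (0.15556) | −0.14813 (0.15263) |
| 10% of V1 also missing, all participants | −0.31809 (0.15428) | −0.15280 (0.15042) |
| Same, pairs only | −0.33068 (0.15900) | −0.14399 (0.15325) |

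With V1 complete, the estimates equal those of ANCOVA on complete pairs. When some V1 values are missing as well (175 pairs, 31 V1-only, 21 V2-only), the V2-only participants do contribute.

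**3. Possible bias.** Everything in this step is assumed except SD 0.7. Let h be the standardised HbA1c response (higher is worse) and ρ its partial correlation with V2 MAGE given V1 MAGE. With a V1–V2 correlation of 0.5, the residual SD is 0.7 × √(1 − 0.25) = 0.606. If missingness follows a logistic model in h in one arm and is unrelated to h in the other:

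bias = ρ × 0.606 × E[h | V2 MAGE observed]

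| Missing MAGE with HbA1c present | E[h \| observed], odds ratio 2 to 3 per SD | Size of bias, ρ = 0.3 to 0.5 |
|---|---|---|
| 5% | −0.034 to −0.051 | 0.006 to 0.015 |
| 10% | −0.066 to −0.098 | 0.012 to 0.030 |
| 20% | −0.129 to −0.186 | 0.023 to 0.056 |

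Example: 0.5 × 0.606 × 0.098 = 0.030. The bias favours a trained arm if its poor responders skip the sensor, and works against it if those in the control arm do. A separate large-sample simulation (about 18% versus 21% missing, residual SD 0.7) gave 0.027, 0.038, 0.065 and 0.092 at ρ = 0.2, 0.3, 0.5 and 0.7. Using HbA1c brought each to 0.003 or less. With equal dependence in both arms, bias was 0.001 or less either way.

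**4. Effect on the claim.** With 61.6 per arm observed (20% of 77 lost), SE ≈ 0.606 × √(2/61.6) = 0.109. At a true effect of 0.30, the chance that the estimate reaches 0.35 is P(Z > 0.05/0.109) ≈ 32%. A favourable bias of 0.006 to 0.030 makes it about 34 to 43%; 0.023 to 0.056 makes it about 40 to 52%.

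**5. Precision.** With a share m of V2 MAGE missing and HbA1c present for all of them, effective n = n_obs/(1 − m·ρ²). At m = 0.2, 61.6 becomes 62.1, 62.7, 64.8 and 68.3 for ρ = 0.2, 0.3, 0.5 and 0.7. Power goes from 79.2% to 79.6, 80.0, 81.2 and 83.2%. These are upper limits.

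**The case against.** - **Missing at random given arm and baseline is a conventional assumption.** The SAP states it and will report missing counts by group and time point. This stands: using HbA1c improves the plan and does not correct an arithmetical or logical error.
- **A reader might infer that the MAGE model is strictly a complete-pair analysis.** The documents do not support that. SAP Section 4 excludes only participants who leave before baseline measurements, so someone with a failed V1 sensor and a valid V2 recording stays in and contributes. V1-only participants inform the common baseline mean, and with it the conditional means and within-group changes. The point is limited to the between-group V2 contrast.
- **A reader might take 20% as the share with HbA1c but no MAGE.** The 20% in Protocol 13.3 is general drop-out. People who leave before week 24 will usually lack V2 HbA1c too, leaving at best the week-12 value. This is why the 5 to 10% rows are the more relevant ones, and why the correction would be less complete in those who left.
- **A reader might infer that many HbA1c-only participants are expected.** The completer definition permits the pattern, but V3 has no MAGE, so some such wording was needed anyway.
- **The mechanism is assumed and one-sided.** No passage says that sensor refusal differs by arm. Staff insert the sensor at the week-24 visit itself, the CGM is blinded, and Protocol 9.9 offers study results only after the study period. This weakens a direct reaction to the V2 result, although perceived control could still matter.
- **A joint model fits awkwardly with the log-transformed, generalised and non-parametric fallbacks in Analysis methods.** True, and a reason to prefer imputation.

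**Conclusion.** The point holds for the between-group MAGE contrast. The single post-baseline value means that likelihood estimation recovers nothing there for participants without V2 MAGE, and HbA1c goes unused. Under the illustrative one-arm mechanism, bias is about 0.01 to 0.03 mmol/l (up to roughly 9% of the 0.35 threshold) if 5 to 10% lack MAGE but have HbA1c, and about 0.02 to 0.06 (up to 16%) if 20% do. It is about zero if missingness is unrelated to HbA1c or related equally in both arms.

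The missing share, the partial correlation and the odds ratio are assumptions, and the direction could be either way. The documents do not show that the planned MAGE result will be biased. The gain in power is small, about 0 to 4 points at 20% missing, so the case rests on a more credible missing-data assumption for a primary outcome that can carry the superiority claim alone. It is a cheap improvement worth making before the analysis is run.

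**What to change.** In SAP, Missing data, add a paragraph for MAGE:

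1. Multiply impute V2 MAGE within each arm from V1 MAGE and HbA1c at V1, week 12 and V2, imputing missing HbA1c in the same step. Then run the planned baseline-corrected contrast, pool the results, and apply the same 0.35 mmol/l rule. An equivalent joint HbA1c–MAGE repeated-measures model is an alternative.
2. Make this the MAGE analysis or, at minimum, a named sensitivity analysis beside the planned model, and say in advance which of the two decides the claim.
3. State that in the univariate model participants without V2 MAGE do not inform the between-group V2 contrast.
4. Report, by arm, how many participants have V2 HbA1c but no V2 MAGE. This shows how much the question matters.

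Cost: SAP wording, an imputation step and some programming. No new data are needed, and the effect measure is unchanged. The SE stays essentially the same, about 0.11 in the simulated scenarios.

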## Additional analyses

Not relevant.

## Harms

Data on harms are not systematically collected and will not be reported.

## Statistical software

SAS Enterprise Guide software version 8.3 or newer (SAS Institute Inc., Cary, NC, USA) and R software version 4.0.2 or newer (R Core Team, R Foundation for Statistical Computing, Vienna, Austria).

